#### 4.2.4. Supplementary Estimands

##### 4.2.4.1. Course of Systemic Corticosteroids for CRSwNP / ECRS Handled as Failure

Supplementary estimands for the two co-primary endpoints will be performed and analysed as detailed within Section 4.2.2, with the summary measure of treatment effect as the difference in mean scores between mepolizumab and placebo.

The main intercurrent events (ICEs) anticipated and how they are to be handled are identical to the co-primary estimands defined within Section 4.2.2, with the exception of:

- Course of systemic CS for CRSwNP / ECRS – to be handled using a composite strategy by incorporating occurrence of the event into the definition of the endpoint. Specifically, participants who receive a course of systemic CS for CRSwNP / ECRS will be handled as a failure and assigned the worst possible score for inclusion in the analysis of all subsequent visits (or 4-week periods) following the initiation of a course of systemic CS. Assessments taking place on the same day as the initiation of a course of systemic CS are assumed to have been carried out before the CS medication.

#### **4.2.4.2. Worst Observed Score Prior to Surgery**

A second supplementary estimand for the two co-primary endpoints will be performed and analysed as detailed within Section 4.2.2, with the summary measure of treatment effect as the difference in mean scores between mepolizumab and placebo.

The main intercurrent events (ICEs) anticipated and how they are handled are identical to the co-primary estimands defined within Section 4.2.2, with the exception of:

- Surgery, which includes any procedure involving instruments resulting in incision and removal of tissue from the nasal cavity (e.g. polypectomy/FESS) – to be handled using a composite strategy by incorporating occurrence of the event into the definition of the endpoint. Specifically, participants who undergo surgery will be assigned the participant's worst observed score prior to the surgery event for inclusion in the analysis of all subsequent visits (or 4-week periods) following surgery. Assessments taking place on the same day as surgery are assumed to have been carried out before the surgery.

## 4.3. Secondary Endpoint(s) Analyses

### 4.3.1. Definition of Endpoint(s)

The secondary endpoints for analysis are:

- Change from baseline in SNOT-22 total score at Week 52
- Change from baseline in mean overall VAS symptom score during the 4 weeks prior to Week 52
- Change from baseline in mean composite VAS score (combining VAS scores for nasal obstruction, nasal discharge, mucus in the throat and loss of smell) during the 4 weeks prior to Week 52
- Change from baseline in mean VAS for loss of smell score during the 4 weeks prior to Week 52
- Change from baseline in Lund Mackay CT score at Week 52
- Time to first nasal surgery or course of systemic CS for CRSwNP / ECRS up to Week 52

#### 4.3.1.1. SNOT-22 Total Score

The 22 questions of the Sino-Nasal Outcomes Test-22 (SNOT-22) questionnaire are each graded on a 6-point scale ranging from 0 = 'CCI [REDACTED]' to 5 = 'CCI [REDACTED] [REDACTED]'. The scores for each of the questions are summed to derive the total score for that participant at that visit, which ranges from 0 to 110 with higher scores representing worse quality of life [Hopkins, 2009].

The primary assessment will be at Week 52. Baseline will be defined as the latest non-missing measurement collected prior to the first dose of study treatment (Section 4.1.2.1).

#### 4.3.1.2. Mean Individual, Overall and Composite VAS Symptom Scores

The collection of six nasal polyposis symptoms VAS scores (one VAS for each symptom and for symptoms overall) are described within Section 4.2.1.2.

Two separate composite VAS scores will be derived using the individual symptom VAS scores. One composite VAS score will be derived using the individual VAS scores of symptoms of (1) CCI [REDACTED], (2) CCI [REDACTED], (3) CCI [REDACTED] and (4) CCI [REDACTED] :

$$\text{Composite VAS score of Nasal Symptoms} = \frac{\text{Sum of the four individual symptoms VAS scores}}{4}$$

A second composite VAS score will be derived using the individual VAS scores of symptoms of (1) CCI [REDACTED], (2) CCI [REDACTED], (3) CCI [REDACTED], (4) CCI [REDACTED] and (5) CCI [REDACTED] :

$$\text{Composite VAS score of Nasal Symptoms and Facial Pain} = \frac{\text{Sum of the five individual symptoms VAS scores}}{5}$$

The composite VAS score of Nasal Symptoms, overall VAS symptom score and individual VAS symptom score of loss of smell will be analysed as secondary endpoints in this study.

#### 4.3.1.3. Lund Mackay CT Score

The Lund Mackay CT scoring system is based on localization with points given for degree of opacification: 0 = **CCI** [REDACTED], 1 = **CCI** [REDACTED], 2 = **CCI** [REDACTED]. These points are then applied to the maxillary, anterior ethmoid, posterior ethmoid, sphenoid, frontal sinus on each side. The osteomeatal complex (OC) is graded as 0 = **CCI** [REDACTED], or 2 = **CCI** [REDACTED]. This scoring system has been validated in several studies [Bhattacharyya, 1999; Lund, 1993]. For patients in whom the OC is missing (because of a previous surgery) the reader should consider the location of the former OC and provide a scoring (as if the OC was there).

A CT scan should be performed anytime during the run-in, and at Week 52 and IP discontinuation/Early Withdrawal Visit. CT scans central reading for Lund Mackay CT score will be used in the statistical analysis. The primary assessment will be at Week 52. Baseline will be defined as the latest non-missing measurement collected prior to the first dose of study treatment (Section 4.1.2.1).

#### 4.3.1.4. Time to First Nasal Surgery or Course of Systemic CS for CRSwNP / ECRS

Nasal polyps surgery is defined as any procedure involving instruments with resulting incision (cutting open) and removal of the polyp tissue from the nasal cavity (polypectomy/FESS). Any procedure involving instrumentation in the nasal cavity resulting in dilatation of the nasal passage such as balloon sinuplasty, insertion of coated stents or direct injection of steroids or other medication without any removal of nasal polyps tissue does not fulfil this surgery criterion. A clinical review will be carried out prior to the unblinding of treatment codes to identify all events to be considered as part of this evaluation.

Courses of systemic CS for CRSwNP / ECRS will be collected as a concomitant medication of systemic corticosteroids (taken via the following routes: oral, intravenous or intramuscular) with a collected reason for concomitant medication of 'Nasal Polyps'.

The time to first nasal surgery or course of systemic CS for CRSwNP / ECRS will be determined as the number of days from the date of first dose of study medication to the date of first event (Nasal Surgery or Course of Systemic CS for CRSwNP / ECRS, whichever is sooner). For participants who complete to Week 52 without experiencing nasal surgery or a course of systemic CS for CRSwNP / ECRS, event times will be censored at the time of the Week 52 visit. If a participant withdraws from the study before Week 52 and before experiencing nasal surgery or having a course of systemic CS for CRSwNP / ECRS, the event time will be censored at the time of study withdrawal.

#### 4.3.2. Main Analytical Approach

The following secondary endpoints will be analysed as detailed for the two co-primary endpoints within Section 4.2.2:

- Change from baseline in SNOT-22 total score at Week 52
- Change from baseline in mean overall VAS symptom score during the 4 weeks prior to Week 52

- Change from baseline in mean composite VAS score (combining VAS scores for nasal obstruction, nasal discharge, mucus in the throat and loss of smell) during the 4 weeks prior to Week 52
- Change from baseline in mean VAS for loss of smell score during the 4 weeks prior to Week 52
- Change from baseline in Lund Mackay CT score at Week 52 (based on ANCOVA analysis)

#### **4.3.2.1. Time to First Nasal Surgery or Course of Systemic CS for CRSwNP / ECRS**

For the endpoint of time to first nasal surgery or course of systemic CS for CRSwNP / ECRS up to Week 52, the treatment effect to be estimated will be the comparison of mepolizumab 100 mg SC + SoC to placebo + SoC. The population of interest will be the entire trial population (patients meeting the study inclusion/exclusion criteria with a diagnosis of CRSwNP / ECRS) who are randomised and receiving study treatment (ITT analysis set) and the summary measure of treatment effect will be the hazard ratio (mepolizumab / placebo). The hazard ratio represents the relative probability of nasal surgery or course of systemic steroids for CRSwNP / ECRS at any time during the study.

[figure not shown]
The anticipated intercurrent events of premature discontinuation of study treatment unrelated to the COVID-19 pandemic, changes in background medication/starting of a prohibited medication unrelated to the COVID-19 pandemic or interruptions of 2 or more consecutive doses to investigational product will be handled using a treatment policy strategy, such that available event times will be included in the analysis regardless of whether the event (surgery or course of systemic CS for CRSwNP / ECRS) occurred before or after discontinuation of study treatment or changes in background medication/starting of a prohibited medication. Data occurring after intercurrent events of premature discontinuation of study treatment or changes in background medication/starting of a prohibited medication related to the COVID-19 pandemic will not be included in the statistical analyses and each participant will be censored at the time of the COVID-19 pandemic related intercurrent event. If a participant withdraws from the study before experiencing nasal surgery or having a course of systemic CS for CRSwNP / ECRS, the event time will be censored at the time of study withdrawal.

Statistical analysis will use the Cox proportional hazards model with covariates of treatment group, log of baseline blood eosinophil count, number of previous surgeries (0, 1, 2, >2; ordinal), background INCS use and country. A log(-log(survival)) plot by treatment group will be used to assess the assumption of proportional hazards.

The number of participants with an event, the number censored due to study withdrawal, due to occurrence of COVID-19 related intercurrent event, and at study completion will be presented by treatment arm. The hazard ratio with corresponding 95% CI and p-value from the Cox proportional hazards model will be presented. Additionally, a summary and graph of the Kaplan-Meier estimates of the cumulative proportion of participants with nasal surgery or a course of systemic CS for CRSwNP / ECRS within each treatment arm over time will be produced.

[figure not shown]

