Study CRT110178 was an investigator-led, collaborative research study of randomised, double-blind, placebo-controlled design comparing mepolizumab versus placebo in participants with severe NPs that were recurrent after surgery. Participants were

randomised to receive two single IV injections (28 days apart) of mepolizumab 750 mg IV (n=20) or placebo (n=10). The primary endpoint was the change from baseline in total endoscopic NP score which was the sum of left and right nostril scores assessed by endoscopy at Week 8 versus baseline. An improvement was observed for mepolizumab patients compared to placebo at Week 8 (-1.22, 90% CI: -2.28, -0.17; one-sided p=0.0258).

Study MPP111782 was a GSK Phase II study that was a two-part (Part A and Part B) randomised, double-blind, placebo controlled, multi-centre study to investigate the use of mepolizumab 750 mg IV versus placebo in reducing the need for surgery in participants with severe bilateral NP refractory to current SoC. All participants were in need of surgery at the start of the study and had at least one prior surgery. Participants were considered in need of surgery if they had an overall VAS symptom score of >7 and an endoscopic NP score of ≥ 3 in at least one nostril. One hundred and five participants were randomised to receive either six 750 mg IV injections of mepolizumab (54 participants) or placebo (51 participants), one injection every four weeks for up to a total of 6 doses in Part A. Participants who no longer required surgery at the end of Part A were given the option to enter Part B where they were followed up for a further 6 months with no treatment. Limited data are available for Part B of the study as only 7 participants in the placebo group and 14 participants in the mepolizumab group entered before Part B was discontinued following a protocol amendment.

The primary endpoint was reduction in the need for surgery at the end of Part A (4 weeks post last dose, Week 25). A significantly greater proportion of participants in the mepolizumab group compared to placebo no longer required surgery at the end of Part A (33% vs 10% respectively, p=0.003). The overall patient-reported VAS symptom scores also supported the efficacy of mepolizumab, with a treatment difference from placebo at Week 25 of -1.78 (95% CI: -2.88, -0.68; p=0.002, PP Population). These improvements were supported by changes in individual VAS symptom scores and SNOT-22, a disease specific measure of HRQoL.

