The current standard of care (SoC) for CRSwNP is treatment with INCS and, for severe symptoms, intermittent courses of systemic corticosteroids, when short term relief is required [Fokkens, 2020]. Antibiotic courses may also be required for intercurrent sinus infection, which often complicates severe NP. Although many patients with NP can be adequately controlled with simple medical care (INCS and OCS, occasional nasal douching and antibiotic courses) [Allobid, 2012; Newton, 2008], progression to surgery as a result of severe symptoms and disruption to quality of life is common. Surgery, when ultimately indicated, involves the removal of the polyp tissue and diseased mucosa, restoring aeration of the nasal passage and sinuses. Over 250,000 NP surgeries are performed in the US annually [Bhattacharyya, 2010]. However, polyps have a strong tendency to recur, often requiring repeat surgery [Levine, 1990; Larsen, 1997; Rucci, 2003; Wynn, 2004; Jankowski, 2006; Brescia, 2015] with a timescale that can vary from a few months to years. Data suggests patients with NP associated with tissue eosinophilia constitute the majority of those who have a recurrence after surgery [Brescia, 2015]. Repeat (revision) surgery is associated with diminishing success and a higher potential for adverse effects [Bhattacharyya, 2004; Chu, 1997], hence alternative treatment options are needed for this patient group.

In Japan, chronic rhinosinusitis (CRS) is recognised as a common chronic disease [Tokunaga, 2015]. In recent years, cases of CRS with NP (CRSwNP) associated with eosinophilic infiltration have increased in Japan due to westernisation of eating habits and environments [Tokunaga, 2015]. Patients are diagnosed as eosinophilic chronic rhinosinusitis (ECRS) using the JESREC (Japanese Epidemiological Survey of Refractory Eosinophilic Chronic Rhinosinusitis) scoring system based on the presence of bilateral NP, CT findings, and eosinophilia in peripheral blood. This scoring system provide a criterion to diagnose and classify ECRS without the use of biopsy or operational specimens. A patient is diagnosed as having ECRS if the JESREC score is 11 points or higher. Additionally, patients CRS is further classified into four groups according to blood eosinophilia, ethmoid-dominant shadow in CT, and comorbidity (bronchial asthma, aspirin intolerance (AI) non-steroidal anti-inflammatory drugs

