A documented blood eosinophil count of over 2% in the 12 months prior to Visit 0 OR through a blood sample taken between Visit 0 and Visit 1. ALL participants must meet blood eosinophil count of over 2% by Visit 1.

Participants with peripheral blood eosinophil count over 2% to 5% must also have comorbid bronchial asthma, aspirin intolerance, or nonsteroidal anti-inflammatory drug intolerance at Visit 1 assessment in order to return for Visit 2.

5. Endoscopic bilateral NP score of at least 5 out of a maximum score of 8 (with a minimum score of 2 in each nasal cavity) assessed by the investigator

6. Participants who have had at least one of the following at Visit 1:

- previous nasal surgery for the removal of NP,
- have used at least three consecutive days of systemic corticosteroids in the previous 2 years for the treatment of NP,
- medically unsuitable or intolerant to systemic corticosteroid

7. Participants with **severe NP** symptoms defined as a nasal obstruction VAS symptom score of >5

8. Presence of symptoms of CRS as described by at least two different symptoms for at least 12 weeks prior to Visit 1, one of which should be either nasal blockage/obstruction/congestion or nasal discharge (anterior/posterior nasal drip), plus

- facial pain/pressure

and/or

- reduction or loss of smell

INFORMED CONSENT

9. Capable of giving signed informed consent which includes compliance with the requirements and restrictions listed in the informed consent form (ICF) and in this study protocol.

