9.4.2. Secondary Endpoint(s)

Endpoint	Statistical Analysis Methods
Secondary	
Estimands for the secondary variables of change from baseline in SNOT-22 total score at Week 52, change from baseline in mean overall VAS symptom score, mean composite VAS score (combining VAS scores for nasal obstruction, nasal discharge, mucus in the throat and loss of smell) and mean VAS for loss of smell score at Week 52 (calculated as the mean of all measurements made in the 4 weeks prior to Week 52), and change from baseline in Lund Mackay CT score at Week 52 will use the same population, summary measure and strategies for intercurrent events as for the primary estimands. Analysis methods will be the same as for the co-primary endpoints.
 
For the endpoint of time to first nasal surgery or course of systemic CS for CRSwNP / ECRS up to Week 52, the summary measure will be the hazard ratio. The anticipated intercurrent events of premature discontinuation of study treatment or changes in background medication/starting of a prohibited medication will be handled using a treatment policy strategy, such that available event times will be included in the analysis regardless of whether the event (surgery or course of systemic CS for CRSwNP / ECRS) occurred before or after discontinuation of randomised treatment or changes in background medication/starting of a prohibited medication. Data impacted by COVID-19 related intercurrent events will not be included in the statistical analyses and each subject will be censored at the time of the COVID-19 related intercurrent event. Statistical analysis will use the Cox proportional hazards model with covariates of treatment group, log of baseline blood eosinophil count, number of previous surgeries (1, 2, >2; ordinal), background INCS use and country. A graph of the Kaplan-Meier estimates of the proportion of participants with events over time will be produced by treatment group. If a participant withdraws from the study before experiencing nasal surgery or having a course of systemic CS for CRSwNP / ECRS, the event time will be censored at the time of study withdrawal.

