**Table 3 Changes to Protocol Defined Analyses**

Protocol Defined Analysis	SAP Defined Analysis	Rationale for Changes
Time to first 'need for surgery' (NP score $\geq 5$ and overall VAS symptom score $>7$ ) up to Weeks 4, 8, 24 and 52	Need for surgery (NP score $\geq 5$ and overall VAS symptom score $>7$ ) at Week 52	It is expected that patients will enter the study with a 'need for surgery' due to requirement to meet inclusion criteria of severe NP symptoms.
Lund Mackay CT score at Week 52 will use the same population, summary measure and strategies for intercurrent events as for the primary estimands. Analysis methods will be the same as for the co-primary endpoints.	Lund Mackay CT score at Week 52 will use the same population, summary measure and strategies for intercurrent events as for the primary estimands. Analysis methods will be based on ANCOVA.	Lund Mackay CT score is recorded once post-baseline at Week 52, therefore assessment of change from baseline via ANCOVA analysis is appropriate.

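### The Cox model for time to first nasal surgery or systemic CS course (H8) omits baseline polyp score and symptom severity; the test is valid, but adding them before unblinding could recover some power at almost no cost

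*SAP*

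**What the plan says.** SAP 4.3.2.1 specifies the H8 model: "Statistical analysis will use the Cox proportional hazards model with covariates of treatment group, log of baseline blood eosinophil count, number of previous surgeries" (with categories "0, 1, 2, >2; ordinal), background INCS use and country"). Protocol 9.4.2 has the same list, except that previous surgeries are coded differently: "number of previous surgeries (1, 2, >2; ordinal), background INCS use and country". Neither list contains an endoscopic NP score or a symptom VAS.

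The continuous endpoints are treated differently. SAP 4.2.2 adjusts each co-primary for its own baseline value, and SAP 4.3.2 analyses the continuous secondary endpoints in the same way (ANCOVA for the CT score).

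On what drives the event, SAP Table 3 defines need for surgery by an NP score of at least 5 "and overall VAS symptom score $>7$ ) at Week 52". The Phase II study described in the Protocol synopsis used the same two measures: "Participants were considered in need of surgery if they had an overall VAS symptom score of >7 and an endoscopic NP score of" at least 3 in one nostril. Protocol 2.2 says that "progression to surgery as a result of severe symptoms and disruption to quality of life is common", and it also describes systemic corticosteroid courses as treatment for severe symptoms.

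**The concern.** H8 has no baseline value of itself, so the rule used for the continuous endpoints gives it no baseline severity score. The model does carry eosinophils, previous surgeries, INCS use and country, but none of these measures how large the polyps are or how bad the symptoms are at randomisation. The documents tie both components of H8 to severity.

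In a Cox model, leaving out a prognostic covariate has two effects even in a randomised trial: the test of treatment loses power, and the estimated hazard ratio moves toward 1. H8 is tested only after H3 to H7 are all rejected, and the sample size was set on the co-primaries alone, so H8 has no stated power. It is also the only multiplicity-controlled endpoint made of clinical events instead of scores.

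The scores are already collected. Central NP score is a randomisation criterion and a co-primary baseline. Overall VAS is recorded in the same daily eDiary as nasal obstruction, with the baseline 7-day mean defined in SAP 4.1.2.2.

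**Working it through.** **1. The plan's own power figures.** They cover the co-primaries only. With 80 per arm, two-sided 5% and a non-central t with 158 df, the non-centrality is difference / (SD × √(2/80)).
- NP score, difference 1.00, SD 1.82: power 93.2%, as stated.
- Nasal obstruction VAS, difference 2.00, SD 3.25: power 97.2%, as stated.

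There is no H8 figure to reproduce.

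**2. Where H8 stands.** Schoenfeld: power = Φ(√(events/4) × |ln HR| − 1.96).
- HR 0.43, 30 events: √7.5 × 0.844 − 1.96 = 0.35, power 64%. With 60 events, 90%.
- HR 0.60: 29% with 30 events, 51% with 60.

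The 0.43 is the previous Phase III trial's result for surgery alone, so it is a scenario for this composite and not an estimate. Event numbers are assumed.

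**3. One omitted covariate.** Exponential event times, 80 per arm, censoring at one year, conditional HR 0.43 or 0.60, placebo risk 25% or 50%, 1,500 trials per cell, model with and without one standard normal covariate:

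| Covariate HR per SD | Power lost by omission | Median fitted HR, omitted vs included |
|---|---|---|
| 1.0 | none (within 1 point) | no change |
| 1.25 | 0 to 2 points | differs by at most about 0.01 |
| 1.5 | 0 to 4 points | 0.43-0.45 vs 0.42-0.43; 0.60-0.61 vs 0.59-0.60 |
| 2.0 | 4 to 8 points | 0.45-0.47 vs 0.42; 0.61-0.63 vs 0.59 |

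**4. Two omitted scores.** Assumptions: 80 per arm, 8% withdrawal, placebo Week 52 risk 30% or 45%, true HR 0.43 or 0.50, scores correlated 0.3, test at two-sided 5%. Monte Carlo error is about 1 point. With a log-HR of 0.5 per SD for each score:

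| Placebo risk, HR | Power without → with | With four non-prognostic covariates in both models |
|---|---|---|
| 30%, 0.43 | 59 → 66% | 59 → 66% |
| 30%, 0.50 | 47 → 53% | 46 → 53% |
| 45%, 0.43 | 75 → 85% | 77 → 86% |
| 45%, 0.50 | 61 → 74% | 61 → 72% |

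In the second version the median HR goes from 0.46, 0.52, 0.47 and 0.54 without the scores to 0.42, 0.48, 0.42 and 0.48 with them. At 0.3 per SD the gain is 2-5 points; if neither score is prognostic, the change is under 1 point. A third version, with eosinophils, surgeries, INCS and two country terms in the comparator, gave 1-2 points at 0.15 per SD, 2-4 at 0.3 and 5-9 at 0.5. Across versions the gain at 0.5 is therefore 5-13 points.

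**5. Why steps 3 and 4 agree.** Two scores with log-HR b each and correlation 0.3 form a predictor with SD √(2b² + 0.6b²).
- b = 0.5: √0.65 = 0.81, HR about 2.2 per SD, just beyond the last row of step 3.
- b = 0.3: √0.234 = 0.48, HR about 1.6 per SD, near the 1.5 row.

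**6. Events available.** Before withdrawal, at 30% risk and HR 0.43: 80 × 0.30 + 80 × (1 − 0.70^0.43) = 24 + 11 = 35. At 45% and HR 0.50: 36 + 80 × (1 − 0.55^0.5) = 36 + 21 = 57. At 45% and HR 1: 72. With true HR 1, rejection was 5-7% with four stand-in covariates in both models, and about 4-7% in the third version.

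**The case against.** The strongest reply is that this is an optional efficiency gain of unknown size. Most of its parts stand.

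- **Prognostic strength is not documented.** A reader might infer that power is certainly lost. The documents do not support that: the loss ranges from nothing upward, depending on a value they do not give.
- **Entry limits narrow the scores.** Protocol 5.1 requires "Endoscopic bilateral NP score of at least 5 out of a maximum score of 8", Protocol 5.3 a mean nasal obstruction VAS above 5, and SAP Table 3 expects patients to enter already in need of surgery. NP scores of 5-8 still leave some spread, but 0.5 per SD for each score implies roughly an 8-fold hazard difference between the 10th and 90th percentiles (exp(2 × 1.28 × 0.81)), beyond what the listed covariates explain.
- **Some severity information is already in the model.** A reader might infer that it has none. Protocol 5.3 uses blood eosinophils in confirming at least moderate disease, and previous surgeries reflect disease history.
- **Nasal obstruction VAS is not the documented driver.** A reader might reach for it because it is co-primary, but both need-for-surgery definitions use the overall VAS.
- **H8 also counts steroid courses.** Protocol 2.2 calls them standard of care for ECRS in Japan, so local practice may drive some events; country captures part of that.
- **The hazard ratio is not biased.** A reader might infer that it is. The adjusted and less-adjusted ratios are different quantities, and the planned randomised test keeps its type I error.

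The remaining argument, that extra terms overload a model with few events and that SAP 4.1.3 already foresees convergence trouble from small countries, is weaker. In the simulations the two terms cost under 1 point of power when not prognostic and showed no clear type I penalty.

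**Conclusion.** The omission is real and the same in both documents. The planned H8 analysis is valid, so this is a worthwhile improvement and not an error. If baseline NP score and symptom severity predict the event beyond the listed covariates, the present model gives up power and reports a hazard ratio nearer 1. With placebo risk 30-45%, HR 0.43-0.50, 80 per arm and the full 5% reaching H8, the gain from adding two scores is about 0 points if they are not prognostic, 2-5 points at 0.3 per SD each, and 5-13 points at 0.5. The lower part of that range is the more cautious expectation, given the entry limits. The consequence is confined to the last controlled secondary claim.

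**What to change.** Before unblinding, add to the H8 model in SAP 4.3.2.1 two continuous covariates: baseline total endoscopic NP score (central read) and baseline 7-day mean overall VAS symptom score. Record the change in SAP Table 3 and keep the present model as a supportive analysis. State that the hazard ratio is conditional on the listed covariates.

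The cost is a short SAP edit, no new data, and two more model terms with roughly 35-70 events. Made after unblinding, the same change would be post hoc.

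The same sentence needs a second entry in Table 3 in any case: previous surgeries are coded from 1 in Protocol 9.4.2 and from 0 in the SAP, and Table 3 does not list that difference.
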